#### **6.5 Definition of End of Trial**

Refer to section 15.

## **6.6 Discontinuation/ Withdrawal of Participants from Study Treatment**

Each participant has the right to withdraw study at any time. In addition, the investigator may discontinue a participant from the study at any time if the investigator considers it necessary for any reason including:

- Non-compliant with the established protocol by moving excessively during the testing
- Ineligibility (either arising during the study or retrospective having been overlooked at screening)
- Significant protocol deviation
- Significant non-compliance with study requirements
- An adverse event which requires discontinuation of the study medication or results in inability to continue to comply with study procedures
- Consent withdrawn

Withdrawn participants will be replaced.

The reason for withdrawal will be recorded in the CRF.

If the participant is withdrawn due to an adverse event, the investigator will arrange for follow-up visits or telephone calls until the adverse event has resolved or stabilised.

## **6.7 Source Data**

CRF entries will be considered source data if the CRF is the site of the original recording (e.g., there is no other written or electronic record of data). In this study the CRF will be used as the source document for weight, height, waist and chest size, and gender.

All documents will be stored safely in confidential conditions. On all study-specific documents, other than the signed consent, the participant will be referred to by the study participant code, not by name.

# **7. TREATMENT OF STUDY PARTICIPANTS**

## **7.1 Description of Study Intervention(s)**

[figure not shown]
The standard pillows used in the ICU were the Sleepsia Bamboo Pillows, 508mm x 660.4mm x 127mm. Each pillow would be placed under the pelvis and chest.

The novel Proning Pillow System is a CE marked device manufactured by Putnam Health Co Ltd ([name]) that includes two separate pillows for the chest and pelvis:

[figure not shown]
Ortho Solutions chest pillow 800 x 300 x 180 mm

Ortho Solutions Pelvic pillow 700 x 300 x 180 mm

**Chest pillow**

**Pelvic pillow**

In each case, a pressure mat (BodiTrak Pro standard, CE 0413) will be placed on each pillow (chest and pelvis). The participant will lie on top of the pillows. The pressure mat will be connected to a laptop which will capture the data using the BodiTrak Pro software.

## **7.2 Maintenance and storage of device**

The pillows, bed and pressure mat will be wiped clean with disinfectant wipes (approved by the Infection Prevention and Control Team) between participants. The pillows will be stored in Aintree hospital.

## **7.3 Concomitant Medication (if applicable)**

N/A

## **8. SAFETY REPORTING**

Definitions for DD, AE, ADE, SAE and SADE are in Section 19.

### **8.1 Reporting of AE**

All AEs occurring during the study observed by the investigator or reported by the participant, whether or not attributed to the device under investigation, will be reported, without undue delay, to the Chief Investigator and LUHFT R&D and recorded on the hospital incident reporting system, in the source data (medical notes) and the CRF. Any questions concerning adverse event reporting should be directed to the Chief Investigator in the first instance.

### **8.2 Reporting of DDs/SAEs/SADEs/USADEs**

All SAEs, SADEs, and USADEs will be reported to the sponsor/legal representative, Chief Investigator and LUHFT R&D immediately; regardless of relationship to the device. DDs that might have led to an SAE if suitable action had not been taken, intervention had not been made or if circumstances had been less fortunate are similarly reported. All SAEs, SADEs and USADEs will be recorded on the hospital incident reporting system, in the source data (medical notes) and the CRF.

Reports of related and unexpected SAEs should be submitted to the Research Ethics Committee (REC) within 15 days of the Chief Investigator becoming aware of the event, using the SAE report form for non-CTIMPs published on the HRA website.

All reporting to LUHFT R&D should be by email to [[contact]](mailto:[contact]) giving as much information about the incident as possible, and should be signed by the PI or Co-investigator. The LUHFT SADE reporting form should be used for LUHFT sponsored studies.

---

 <https://www.hra.nhs.uk/approvals-amendments/managing-your-approval/safety-reporting/>, accessed 16/Aug/2021

The LUHFT R&D Department will undertake an initial review of the information and ensure it is reviewed by LUHFT. Events will be followed up until resolution, any appropriate further information will be sent by the research team in a timely manner.

Reporting to the MHRA will be done in liaison with the Chief Investigator.

### **8.3: Annual Reports**

In addition to the above reporting the Chief Investigator will submit once a year, throughout the trial, or on request a progress/safety report to the REC and R&D.

## **9. STATISTICS**

### **9.1 Description of Statistical Methods**

A model-based approach will be used to test the hypothesis. This approach considers complexities such as repeated measurements, unbalanced observations and determination of the magnitude of effects. The model incorporates the measured peak pressure for each participant at each anatomic location (chest and pelvis) and the two different pillow systems (new and standard).

### **9.2 The Number of Participants**

Based on the complexity of the model used to test the experimental hypotheses, and the fact that the sample size should be of the order of 10 times the number of parameters estimated by the model [Harrell], we estimate a sample size of 50 is required.

### **9.3 The Level of Statistical Significance and Model Validation**

Considering the small sample size and the complexity of the model, a significance level of 0.01 will be considered for rejection of the null hypotheses of no difference between peak pressures, with the aim to control the false discovery rate [Harrell]. However, since it is generally recognised that statistical significance alone doesn't necessarily provide a realistic picture of the underlying processes generating the data [Harrell], other measures of quality of the statistical inference will be reported, namely approximate confidence intervals, Akaike Information Criterion, and analysis of residuals.

### **9.4 Procedure for Accounting for Missing, Unused, and Spurious Data.**

The chosen statistical methods can be applied even with unbalanced observations (i.e. outcomes need not be observed for all possible combinations of the experimental factors pillow and position) [Pinheiro]. Due to the nature of the experimental design and the type of

measurements involved, no missing, unused, or spurious data are expected.

## **9.6 Procedures for Reporting any Deviation(s) from the Original Statistical Plan**

Any deviation(s) from the original statistical will be described and justified in protocol and/or in the final report, as appropriate.

## **9.7 Inclusion in Analysis**

All eligible participants

## **10. DIRECT ACCESS TO SOURCE DATA/DOCUMENTS**

Direct access will be granted to authorised representatives from the sponsor, host institution and the regulatory authorities to permit trial-related monitoring, audits and inspections.

## **11. QUALITY CONTROL AND QUALITY ASSURANCE PROCEDURES**

The study will be conducted in accordance with the current approved protocol, ICH GCP, relevant regulations and standard operating procedures.

Regular monitoring will be performed according to ICH GCP. Data will be evaluated for compliance with the protocol and accuracy in relation to source documents. Following written standard operating procedures, the monitors will verify that the clinical trial is conducted and data are generated, documented and reported in compliance with the protocol, GCP and the applicable regulatory requirements.

## **12. ETHICS**

### **12.1 Declaration of Helsinki**

The Investigator will ensure that this study is conducted in accordance with the principles of the Declaration of Helsinki.

### **12.2 ICH Guidelines for Good Clinical Practice**

The Investigator will ensure that this study is conducted in full conformity with relevant regulations and with the ICH Guidelines for Good Clinical Practice R2

### **12.3 Approvals**

The protocol, informed consent form, participant information sheet and any proposed advertising material will be submitted to the Health Research Authority. Local approvals will be sought from participating NHS organisations and the sponsor.

The Chief Investigator will submit and, where necessary, obtain approval from the above parties for all substantial amendments to the original approved documents.

#### **12.4 Participant Confidentiality**

The study staff will ensure that the participants' anonymity is maintained. The participants will be identified only by a participants ID number on the CRF and any electronic database. All documents will be stored securely and only accessible by trial staff and authorised personnel. The study will comply with the Data Protection Act 2018 which requires data to be anonymised as soon as it is practical to do so.

#### **12.5 Other Ethical Considerations**

N/A

### **13. DATA HANDLING AND RECORD KEEPING**

Data will be processed under the terms of UK data protection law (including the UK General Data Protection Regulation (UK GDPR) and the Data Protection Act 2018).

All study data will be entered on a password-protected Microsoft Excel spreadsheet. Once all data has been captured, the spreadsheet will be locked as read-only to protect the integrity of the data.

All pseudonymous data will be stored on a laptop and on the Clinical Engineering LUHFT departmental network.

The participants will be identified by a study specific participants number and/or code in any database. The name and any other identifying detail will NOT be included in any study data electronic file. A copy of the final published results of the study will be sent to the participants should they wish.

## **14. FINANCING AND INSURANCE**

LUHFT ICU will loan a set of pillows for this study. The pressure mats will be supplied by the Posture and Mobility Service in Bryn-y-Neuadd hospital.

NHS bodies are legally liable for the negligent acts and omissions of their employees. If you are harmed whilst taking part in a clinical trial as a result of negligence on the part of a member of the study team this liability cover would apply.

Non-negligent harm is not covered by the NHS indemnity scheme. LUHFT, therefore, cannot agree in advance to pay compensation in these circumstances. In exceptional circumstances an ex-gratia payment may be offered.

## **15. END OF STUDY DEFINITION**

End of study definition would be when the set of number of participants have been recruited and completed all elements of the study and data has been analysed.

## **16. PUBLICATION POLICY**

Authors will be defined as those who have made:

- Substantial contributions to the conception or design of the work; or the acquisition, analysis, or interpretation of data for the work; **AND**
- Drafting the work or revising it critically for important intellectual content; **AND**
- Final approval of the version to be published; **AND**
- Agreement to be accountable for all aspects of the work in ensuring that questions related to the accuracy or integrity of any part of the work are appropriately investigated and resolved.

Contributors who have contributed materially to the paper but whose contributions do not justify authorship will be described clearly in acknowledgements

## **17. ARCHIVING**

Following analysis, data will be fully anonymised then stored in electronic format in Clinical Engineering LUHFT departmental network for at least 15 years. The data will be stored for future ethically approved studies. Archiving will be in line with the sponsor's Standard Operating Procedures.

## 19. APPENDIX

### 19.1 Definitions

#### 19.1.1 Device Deficiency (DD)

This is the inadequacy of a medical device with respect to its identity, quality, durability, reliability, usability, safety or performance. Device deficiencies include malfunction, use error and inadequate labelling.

#### 19.1.2 Adverse Event (AE):

Any untoward medical occurrence, unintended disease or injury or any untoward clinical signs (including an abnormal laboratory finding) in subjects, users or other persons, whether or not related to the investigational medical device and whether anticipated or unanticipated.

This includes events related to the investigational device or the comparator and events related to the procedures involved (any procedure in the study protocol). For users or other persons, i.e. where the medical occurrence, unintended disease or injury is not in the subject, this definition is restricted to events related to the use of investigational medical devices or comparators.

No potential AEs are identified.

#### 19.1.3: Adverse Device Effect (ADE)

Adverse event related to the use of an investigation medical device. This includes AEs resulting from insufficient or inadequate instructions for use, deployment, implantation, installation, or operation, or any malfunction of the investigational medical device. This includes the comparator if the comparator is a medical device.

All AEs judged by either the reporting medically qualified professional or the sponsor as having a reasonable suspected causal relationship to the device qualify as ADEs. For guidance on causality assessment, refer to MEDDEV 2.7/3 Clinical Investigations: Serious Adverse Event Reporting Under Directive 90/385/EEC and 93/42/EEC.

#### 19.1.4: Serious Adverse Event (SAE):

SAE is an adverse event that led to any of the following:

- death

- foetal distress, foetal death or congenital abnormality or birth defect including physical or mental impairment.
- serious deterioration in the health of the subject, users or other persons as defined by one or more of the following:
  - a life-threatening illness or injury
  - a permanent impairment of a body structure or a body function including chronic diseases
  - in-patient or prolonged hospitalisation
  - medical or surgical intervention to prevent life-threatening illness or injury, or permanent impairment to a body structure or a body function

Planned hospitalisation for a pre-existing condition, or a procedure required by the Study Protocol, without serious deterioration in health, is not considered a serious adverse event.

#### **19.1.5: Serious Adverse Device Effects (SADE):**

Adverse device effect that has resulted in any of the consequences of a SAE. This includes device deficiencies that might have led to a SAE if (a) suitable action had not been taken or (b) intervention had not been made or (c) if circumstances had been less fortunate. These are handled under the SAE reporting system. All cases judged by either the reporting medically qualified professional or the sponsor.

#### **19.1.6: Unanticipated Serious Adverse Device Effect (USADE):**

Any serious adverse device effect which by its nature, incidence, severity or outcome has not been identified in the current risk assessment.

## **19.2 Description of Statistical Methods**

Suggested statistical approach in more detail.

A model-based approach to hypothesis testing will be applied. This allows incorporation of complexities such as repeated measurements, nested classification factors, unbalanced observations, and determination of the magnitude of effects [Harrell]. The chosen model belongs to the family of linear mixed-effects models [Pinheiro], and it is formulated as follows:

$$\mathbf{y}_{ij} = \mathbf{X}_{ij}\boldsymbol{\beta} + \mathbf{Z}_{i,j}\mathbf{b}_i + \mathbf{Z}_{ij}b_{ij} + \epsilon_{ij}, \quad i = 1, \dots, M, \quad j = 1, 2$$

$$\mathbf{b}_i \sim N(0, \boldsymbol{\Psi}_1), \quad b_{ij} \sim N(0, \sigma_2^2), \quad \epsilon_{ij} \sim N(0, \sigma^2 \mathbf{I})$$

where  $\mathbf{y}_{ij}$  is the measured peak pressures for subject  $i$  from a sample of size  $M$ , at anatomic location  $j$  (corresponding to chest and pelvis.) The fixed-effects treatment contrast matrices  $\mathbf{X}_{ij}$  encode the experimental factor pillow type (new versus standard).  $\mathbf{Z}_{i,j}$  represents the design matrices of the level-1 random effects for subject  $i$  on the measurements for anatomic location  $j$  within subject  $i$ .  $\mathbf{Z}_{ij}$  represents the design matrices of the level-2 random effects for anatomic location  $j$  within subject  $i$ . The normally distributed  $\mathbf{b}_i$  are assumed to be independent for different  $i$ ; and the normally distributed  $b_{ij}$  are assumed to be independent for different  $i$  or  $j$  and to be independent from  $\mathbf{b}_i$ ; finally, the within-group errors  $\epsilon_{ij}$  (which represent all the variability which is not explained by the model) are assumed to be independent for different  $i$  or  $j$  and to be independent from the random effects. The parameters to be estimated by the above model are represented by the 2-vector  $\boldsymbol{\beta}$ , the variance  $\sigma_2^2$ , and the entries of the 2x2 matrix  $\boldsymbol{\Psi}_1$  (it should be noted that since the latter is a covariance matrix which is forced to be positive definite by construction, only 2 entries need to be estimated.) The total number of parameters is therefore 5.

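### Section 19.2 wrongly says a 2×2 covariance matrix needs only two entries, leaves the random-effects design unwritten, and has no term for a pillow effect that differs between chest and pelvis

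*Combined protocol and SAP*

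**What the plan says.** Section 19.2 specifies a linear mixed model for peak pressure.

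- **Fixed part.** Pillow type enters through "The fixed-effects treatment contrast matrices" X_ij. "The parameters to be estimated by the above model are represented by the 2-vector" β, plus σ₂² and the entries of Ψ₁. No location or pillow-by-location coefficient is listed, and no reference pillow is named.
- **Participant level.** The random vector b_i has a 2×2 covariance matrix Ψ₁. Because that matrix is positive definite, the section says, "only 2 entries need to be estimated".
- **Location within participant.** Z_ij "represents the design matrices of the level-2 random effects for anatomic location" j within participant i. The effect b_ij is a scalar with one variance, σ₂².
- **Count.** "The total number of parameters is therefore 5". Section 19.2.1 multiplies this by 10 to reach M = 50.

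Z_i,j and Z_ij are described in words but never written out. Section 19.2.2 tests β₂ at 0.01. Sections 9.3 and 19.2.2 add "approximate confidence intervals, Akaike Information Criterion, and analysis of residuals" as measures to report. The primary objective in Section 5.1 names both chest and pelvis.

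**The concern.** The only decision rule is the test of β₂, and the confidence interval uses the same standard error. That standard error depends on the random-effects structure, which the plan justifies with an incorrect statement and does not write out.

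Two free entries in Ψ₁ require a constraint that the plan does not name. The simplest is a diagonal matrix. If Z_i,j is coded like X_ij, a diagonal Ψ₁ with entries a and b implies:

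- Var(reference pillow) = a
- Var(other pillow) = a + b
- Cov = a

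The non-reference pillow must then vary between people at least as much as the reference pillow. Exchanging the reference can change the standard error and p-value from the same data. Section 4 gives a reason why this could matter: the new system is meant to sink less under heavier people, so it might vary less between people than the standard pillow.

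Separately, a person whose load moves from chest to pelvis on one pillow has a pillow effect that differs by site. The model can only put that into σ².

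**Working it through.** **The plan's own figure.** 2 (β) + 1 (σ₂²) + 2 (Ψ₁) = 5, and 10 × 5 = 50. Both reproduce. The step that fails is the 2 for Ψ₁. A symmetric 2×2 matrix has two variances and one covariance, that is 3 entries. Positive definiteness limits their range (covariance² < product of the variances) but removes none. The count also leaves out σ².

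**Inputs.** From the documents: M = 50, two locations, two pillows, three repeats per pillow (Section 6.4.5) and a significance level of 0.01, taken as two-sided. The plan does not say whether all three repeats enter y_ij; I assume they do. It gives no SDs, so these are assumptions: participant SD 20 on standard and 10 on new, correlation 0.8, residual SD 17, and location-within-participant SD 5 (10 as an alternative).

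**Correct variance of one participant's mean new-minus-standard difference.** Each pillow mean uses 6 values:

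400 + 100 − 2 × 0.8 × 20 × 10 + 2 × 289/6 = 180 + 96.3 = 276.3

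**Variance under each form of Ψ₁.** Each form was fitted by maximum likelihood to the assumed covariance. SE ratio = √(fitted variance / 276.3). Size = 2Φ(−2.576 × ratio).

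| Ψ₁ | Fitted variance | SE ratio | Size at nominal 1% |
|---|---|---|---|
| Diagonal, treatment-coded, standard as reference | 210.9 | 0.87 | 2.4% |
| Diagonal, treatment-coded, new as reference | 306.8 | 1.05 | 0.7% |
| Diagonal, pillow indicators | 505.4 | 1.35 | 0.05% |
| Common variance plus covariance | 276.3 | 1.00 | 1.0% |
| Unstructured | 276.3 | 1.00 | 1.0% |

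With location SD 10, the three diagonal rows become 0.89, 1.05 and 1.08. The indicator-coded figure is therefore sensitive to that assumption. In that form only the location intercept can carry correlation between the pillows.

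**Range for the treatment-coded diagonal form.**

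- SDs 20 and 15 give about 0.91 and 1.01. SDs 20 and 18 give 0.95 and 0.98. With equal SDs the reference makes no difference.
- With SDs in the ratio 1.5 to 1 and residual SD half the smaller one, the ratios are 0.98 and 1.01.
- Over SD ratios 0.5 to 3, correlations 0.3 to 0.9 and residual SDs 0.3 to 2 (in units of the standard-pillow SD), the SE ratio runs from 0.82 to 1.11 and the size from 0.4% to 3.6%.
- In one simulated dataset the two references gave 0.1368 and 0.1411. The unstructured fit gave 0.1397 under both, equal to the paired standard error.

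**Site-specific pillow effects.** Suppose a participant's pillow effect is higher by s at the chest and lower by s at the pelvis. Let s have SD w, let the residual SD be 12 and let there be no participant-level pillow variation. Within a participant, 10 contrasts then estimate the residual: 8 from repeats and 1 for pillow, each with expectation σ², and 1 for pillow-by-location, with expectation σ² + 3w². The pooled estimate is σ² + 0.3w². The fitted variance of the difference is σ²/3 + w²/10, against a correct σ²/3 = 48.

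- w = 10: 48 + 10 = 58; ratio √(58/48) = 1.10; 48/58 = 0.83, like losing 17% of the sample.
- w = 20: 48 + 40 = 88; ratio √(88/48) = 1.35; 48/88 = 0.55, like losing 45%.

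These ratios are the same under every form of Ψ₁ above. Now let participants also differ in their average pillow effect, with variance τ². The other nine contrasts pool to σ²/3 + w²/9 on the same scale. With equal pillow variances and an unstructured Ψ₁, the inflation therefore disappears once τ exceeds about w/3. At τ = 10 the ratio is 1.00 for either w.

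**The case against.** The strongest reply is that the plan never calls Ψ₁ diagonal. It applies the term treatment contrast only to X_ij, and its remark about two entries gives a reason for a count without stating a constraint. The remark may be a miscount of an unstructured matrix. A common variance plus one covariance also has exactly two free entries. Both forms gave a ratio of 1.00. This stands: a reader might infer that the planned test necessarily depends on the reference pillow, and the text does not support that.

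Second, the magnitudes rest on assumed SDs, and a 2 to 1 ratio is not mild. The two problems also pull apart. The case that makes the first large implies a participant-level pillow SD of √180 = 13.4, and with variation of that order the second has little effect. This stands too, so the two errors should not be added together.

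Third, the absence of a chest-versus-pelvis contrast comes first from the two-element β, not from the random effects alone. Z_ij is not written out, so reading b_ij as an intercept is itself an inference, though one scalar with one variance points that way. In balanced data β₂ still estimates the chest–pelvis average without bias.

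The planned residual analysis and Akaike criterion could reveal a poor covariance fit. No rule says that the model would change as a result, so they do not settle the point.

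**Conclusion.** The stated reason for estimating two entries is wrong, and the random-effects design is not specified well enough to fix the standard error of β₂. Both follow from the text with no assumption.

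The consequence for the test is conditional. If Ψ₁ is fitted as diagonal, the standard error is generally wrong, in either direction: about 0.87 or 1.05 by reference pillow in the assumed case, about 1.35 with indicator coding at location SD 5, and a few percent or less in milder cases. If it is fitted unstructured, or with a common variance plus a covariance, the error is absent in these cases.

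The missing site-specific terms hold on the direct reading of Section 19.2. Their effect on the standard error is conservative (1.10 to 1.35 for shifts of SD 10 to 20) when participant-level pillow variation is near zero, and small otherwise. The more certain loss is that no chest or pelvis result can be given, although the objective names both.

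Two further inferences go too far. A reader might conclude that the false-positive rate will exceed 1%; that needs the diagonal reading, an unfavourable reference and unequal variances. A reader might also conclude that a paired t-test must replace the mixed model. An unstructured Ψ₁ restores the standard error in the first problem, and one averaged difference per person would still give no site-specific result.

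**What to change.** In Sections 9.1 and 19.2, keep the mixed model as the primary analysis and:

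1. Write out Z_i,j and Z_ij, name the reference pillow, and say that all three repeats enter as separate values. With one value per cell, a level-2 pillow term cannot be separated from the residual.
2. Fit Ψ₁ unstructured (3 entries) and delete the statement that positive definiteness leaves two.
3. Add fixed location and pillow-by-location terms. Code location as ±½ so that β₂ is the pillow effect averaged over chest and pelvis, and report the effect at each site.
4. Give the level-2 effect a pillow term as well as an intercept, with a covariance between them. Otherwise the dependence on coding returns at that level.
5. For participants with complete data, report the paired new-minus-standard difference (t with 49 df if all 50 are complete) as a check on the standard error.
6. Restate the parameter count. As written here it is 4 fixed + 3 + 3 + 1 = 11, including σ². The justification of M by 10 per parameter then needs rewording. The rule is a heuristic, so this does not by itself show that 50 is too few.

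The cost is protocol wording and a few lines of code, with no new data. The downside is a few more fixed and covariance parameters, so the plan should name in advance a simpler form to use if the fit does not converge.

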#### **4. BACKGROUND AND RATIONALE**

During the COVID-19 pandemic, intensive care units (ICUs) across the country have been inundated with increasing numbers of COVID patients. Hypoxic patients in ICU require mechanical ventilation and this can be improved by proning these patients to improve oxygenation and prevent ventilator-induced lung injury (Guerin et al, 2013). Standard practice is to use standard hospital pillows to support the pelvis and chest of the patient while they are proned. These pillows do not provide much support to the patients and often need to be adjusted due to the patient 'sinking' into them. Prolonged pronation also leads to pressure sores in these anatomical locations which burden the Trust financially and also cause distress to patients.

A new proning pillow system was developed by [name] and manufactured for the ICU in Aintree hospital which is made from polyurethane memory foam designed to relieve pressure on the patients and prevent pressure sores that often occur during prolonged proning. The pillow system is also designed to withstand the load of heavier patients and reduce the risk of 'sinking' into the pillows when proned for long periods of time.

The aim of the study is to compare the performance of the new proning pillow system with standard pillows, particularly in relation to the risk of pressure sores, by evaluating differences in chest and pelvis interface pressures between the two pillow types. This will be done by having healthy NHS staff lie on the pillows in the prone position for a short period of time while recording the pressure distribution on the pillows using pressure mats placed between them and the pillows. This will help understand the relative risk of pressure sores developing when the new pillow system is used. It is hypothesised that the new pillow system does not increase the risk of pressure sores developing.

The new proning pillow system is a Class 1 CE marked medical device. The proning pillow system consists of a chest pillow and a pelvis pillow made from memory foam designed to reduce contact pressures and peak interface pressures in patients and allow patients to be placed in neutral position for ventilation.

This research is to be submitted in fulfilment of an academic qualification, a Masters of Science in Clinical Sciences (Clinical Engineering). The student will be doing this project under supervision. The student will recruit participants, take informed consent and take measurements.

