## 5. OBJECTIVES

### 5.1 Primary Objective

To evaluate any differences in chest and pelvis interface pressures between novel proning pillows and standard pillows used in ICU.

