### 19.2.2 The Level of Statistical Significance and Model Validation

Considering the small sample size and the complexity of the model, a significance level of 0.01 will be considered for rejection of the null hypotheses of no difference between peak pressures (as represented by parameter  $\beta_2$ ), with the aim to control the false discovery rate [Harrell]. However, since it is generally recognised that statistical significance alone doesn't necessarily provide a realistic picture of the underlying processes generating the data [Harrell], other

measures of quality of the statistical inference will be reported, namely approximate confidence intervals, Akaike Information Criterion, and analysis of residuals.

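### The only planned test averages the pillow effect over chest and pelvis, so a higher peak at one site can be hidden although the objective names both sites

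*Combined protocol and SAP*

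**What the plan says.** Section 5.1 gives the objective: "To evaluate any differences in chest and pelvis interface pressures between novel proning pillows and standard pillows used in ICU". The study title in the synopsis also names both sites.

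Section 9.1 says the model incorporates the peak pressure of each participant "at each anatomic location (chest and pelvis) and the two different pillow systems (new and standard"). Sections 9.4 and 19.2.3 speak of "combinations of the experimental factors pillow and position", so position is treated there as a factor of the experiment.

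Section 19.2 writes the model out. Its fixed-effects matrices "encode the experimental factor pillow type (new versus standard"). On the parameter count it says "The parameters to be estimated by the above model are represented by the 2-vector" β, one level-2 variance and two entries of the subject-level covariance matrix, which makes 5. Anatomic location appears only through b_ij, a level-2 random effect with mean zero and a single variance.

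Section 19.2.2 sets the level of 0.01 for "rejection of the null hypotheses of no difference between peak pressures (as represented by parameter" β₂). No section gives a pillow-by-location term, a contrast for one site, or a separate analysis by site.

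**The concern.** Section 4 states "Prolonged pronation also leads to pressure sores in these anatomical locations", meaning the pelvis and the chest, and adds: "It is hypothesised that the new pillow system does not increase the risk of pressure sores developing". The harm in question is local. A lower peak under the chest does not relieve a higher peak under the pelvis. The new system is also two separate pillows of different lengths (section 7.1), so equal effects at the two sites cannot be taken for granted.

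A test of one average can go wrong in two ways. Opposite effects offset each other, and an effect confined to one site is halved. The study could follow its plan exactly and report no difference, or a benefit, while the peak is higher at one site. A site analysis added after the results were seen would have no planned error control.

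**Working it through.** **1. The plan's own figure.** By the count in section 19.2, 2 (β) + 1 (σ₂²) + 2 (Ψ₁) = 5 parameters. The rule of 10 per parameter in section 19.2.1 gives 10 × 5 = 50, which reproduces. I use the plan's way of counting throughout.

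**2. What β₂ estimates.** The design matrices are not written out. Since X encodes only pillow type and β₂ is the tested difference, β is read as (intercept, pillow). Each participant is measured at 2 sites, on 2 pillow sets, 3 times each (section 6.4.5). In this balanced layout

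β₂ = (chest difference + pelvis difference) / 2, each difference being new minus standard.

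| Chest | Pelvis | β₂ |
|---|---|---|
| −6 | +6 | 0 |
| −8 | +3 | −2.5 |
| −8 | 0 | −4 |

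A rise of h at one site is hidden, or shown as a benefit, whenever the other site falls by h or more. In 150 simulated REML fits of the planned model per scenario, β₂ equalled the mean of the two site differences to within 2 × 10⁻¹⁴ every time.

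**3. The random effects do not help.** b_i and b_ij both have mean zero, so neither can represent a pillow effect that differs systematically by site. The missing location main effect does not bias β₂ in balanced data. It only moves a chest–pelvis gap g into the variance components (σ₂² rises by about g²/2).

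**4. Illustration of size.** The documents give no standard deviations, so these are assumed: residual SD s = 5; participant-level SD of the pillow effect τ = 3, 6 or 9, shared by both sites; M = 50; two-sided 0.01; noncentral t with 49 df.

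- SE of β₂ = √((τ² + s²/3)/50). For τ = 6: √((36 + 8.33)/50) = 0.94.
- SE at one site = √((τ² + 2s²/3)/50). For τ = 6: √((36 + 16.67)/50) = 1.03.

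| Chest/pelvis effect | Test | τ = 3 | τ = 6 | τ = 9 |
|---|---|---|---|---|
| −6/+6 | β₂ | 1% | 1% | 1% |
| −6/+6 | either site alone | 100% | 99.9% | 94% |
| −8/+3 | β₂ (as a benefit) | 94% | 50% | 22% |
| −8/+3 | pelvis alone | 93% | 60% | 31% |

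REML fits of the planned model gave 93%, 48% and 27% for β₂ under −8/+3.

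**5. Sensitivity.** Step 4 assumes that the pillow effect has no further participant-by-site variation. With an SD ω for that variation, ω² is added to the site variance and ω²/2 to the pooled variance. Detection of the +3 at the pelvis is then 73% / 46% / 26% at ω = 4 and 34% / 25% / 17% at ω = 8. The −6/+6 site rate at τ = 9 falls from 94% to 74% at ω = 8. β₂ still rejects in only 1% under −6/+6.

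**The case against.** The strongest reply is that β₂ is a valid and, in balanced data, unbiased estimate of the site average. Its type I error is not shown to be wrong, and no data are lost, because a mat lies on each pillow. Nothing forbids reporting by site, and section 9.6 provides for declared deviations. This is a single-visit study in healthy staff. All of that stands. The planned test is not invalid; it answers a different question from the stated one.

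The text can also be read generously. The appendix calls its approach suggested, hypotheses are mentioned in the plural, and sections 9.1 and 9.4 imply that location was meant to count. Residual analysis might expose a site pattern. But this is the only model written down, M = 50 rests on its parameter count, and β₂ is the only parameter named for the test. An informal look at residuals is neither an estimate nor a test.

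Nothing in the documents suggests that effects are opposite in sign. Both new pillows are memory foam and 180 mm deep, and the effect pairs above were chosen to show cancellation. This is fair: the harm is a possibility, not a prediction. The detection rates also depend on the assumed SDs and fall when participant-by-site variation is allowed, so they should be quoted only with that condition.

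Finally, testing for no difference when the hypothesis is of no increase in risk is a separate issue and carries no weight here.

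**Conclusion.** The concern holds. The sole planned test of the sole objective is of the average of the chest and pelvis effects, and no section supplies a result for either site. The averaging is exact in balanced data and does not depend on any variance. It rests only on reading the 2-vector β as intercept and pillow, which is what the text supports. The percentages are illustrative; neither the conclusion nor the repair depends on them. Because the plan could be followed to the letter and give false reassurance about one site, it should be changed before any data are seen.

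**What to change.** **Model (9.1, 19.2).** Make β a 4-vector: intercept, pillow, location, pillow-by-location. Report the new-minus-standard difference for chest and for pelvis, each with a 99% confidence interval.

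**Error control (9.3, 19.2.2).** Two unadjusted tests at 0.01 would have a family-wise error of 1 − 0.99² = 0.0199 if independent. One option is a joint 2-df test at 0.01, followed if significant by each site at 0.01. In 40,000 simulated runs its family-wise error was 0.6% to 0.9% with no effect at either site, and about 1.0% when only one site differed.

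**Unit of analysis.** Add a pillow term at level 2, or analyse each participant's mean of the 3 repeats. If the interaction is added but b_ij stays scalar, its type I error at nominal 1% is 2%, 5% and 16% for ω = 2, 4 and 8 (with s = 5). This concerns the repair and is not a fault of the planned β₂ test.

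**Sample size basis (9.2, 19.2.1).** By the plan's count the larger model has 4 + 1 + 2 = 7 parameters, or 4 + 2 + 2 = 8 with pillow at level 2. The rule would then give 70 to 80, so the basis for M = 50 must be restated, for example as the precision expected over a range of SDs.

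**Alternative.** Fit the model separately at each site with Holm control (0.005, then 0.01). Each has 2 + 2 = 4 parameters, so the existing rule gives 40, below 50. This is the smaller change.

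**Cost.** Wording in 9.1 to 9.3 and 19.2 to 19.2.2; no new measurements. The site SE is 1.22, 1.09 and 1.05 times the pooled SE at τ = 3, 6 and 9 (1.35, 1.24 and 1.15 at ω = 8). It is at most √2 = 1.41 times if the sites have equal variance and non-negative correlation. If the effect is −4 at both sites, under the step 4 assumptions, the joint test rejects in 100% / 88% / 50%, against 100% / 94% / 62% for β₂.
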